4.2.1 Primary Outcome Measures

The **primary outcomes** will be feasibility and acceptability of the intervention.

Feasibility measures. To assess study feasibility, banner ad click-through rate, number of individuals recruited per week, and the percentage of individuals who were eligible; assented; dropped out and lost to follow-up will be calculated. To assess the feasibility of the media literacy

Purpose	Construct or Behavior	Baseline	Intervention	Post Intervention	Follow-up
Feasibility	Study recruitment	x			
	Study retention			x	x
	Intervention metrics		x	x	
Acceptability	Webpage ratings		x		
	Satisfaction survey			x	
Preliminary Efficacy	Sexual risk behaviors	x			x
	Antecedents to sexual risk	x		x	x
	Media literacy	x		x	x
	Sexual health knowledge	x		x	x

intervention we will calculate intervention metrics (i.e., time spent on each piece of intervention content, percentage who complete all intervention content).

Acceptability measures. To assess acceptability, media literacy intervention participants will be asked to complete content ratings on each piece of intervention content using a 5-star rating system. Participants will also be given the option of providing written feedback on each piece of content as well. All participants will also be asked to complete a satisfaction survey at the post-intervention follow-up.⁴⁸ Participants will be asked to report on study procedure acceptability (e.g., acceptability of recruitment, consent, assessment procedures). Intervention participants will be asked to report how informative, interesting, and helpful the intervention was; how likely they would be to recommend it to friends; and if they have suggestions for how it could be improved. Participants in the control group will be asked which website they went to, if any, and to report how informative, interesting, and helpful the website was; as well as how likely they would be to recommend it to friends. The satisfaction survey will include a combination of likert scale and open-ended responses.

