Other considerations: Mental health and substance use. As mental health and substance use issues are prevalent among ASMM, we will provide all participants with links and phone numbers for LGBT-specific services (e.g., the National Alliance on Mental Health LGBTQ website, PRIDE Institute Substance Use Treatment website, GLBT National Youth Talkline phone number, Trevor Helpline Crisis Intervention for LGBTQ Youth phone number). Although none of the proposed measures specifically ask about reportable issues, the satisfaction survey for the intervention will include open-ended responses. The PI will check these open-ended responses daily in the unlikely event that a participant reports any indication of current, ongoing abuse or neglect of children or elders and/or of imminent danger to self or a specified individual as these indications will have to be considered for clinical intervention and mandated reporting to the appropriate authorities. Daily checks will be documented via PI initials on a study calendar.

Other considerations: Website developer training. To ensure the website developer is informed of research ethics and participant confidentiality they have completed on-line CITI Human Subjects Protection training and signed an

agreement to keep all participant information confidential. The developer has a background in designing/programming websites for research purposes, thus have completed these trainings and signed research confidentiality agreements before.

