	Perceived norms of SEOM behavior	x		x	x
	Expectancies about SEOM behavior	x		x	x
	Perceived consequences of SEOM behavior	x		x	x
Preliminary Efficacy	Sexual risk behaviors	x			x
	Antecedents to sexual risk	x		x	x
	Media literacy	x		x	x
	Sexual health knowledge	x		x	x

will be assessed using the PHQ-4. *Sexual abuse history* will be assessed using the sexual abuse subscale of the Childhood Trauma Questionnaire (CTQ). *Sexual education exposure*. Sources of sexual education (e.g., parents, school, online) and coverage male-male sexual health-related topics will be assessed.¹⁵

Feasibility measures. To assess study feasibility, banner ad click-through rate, number of individuals recruited per week, and the percentage of individuals who were eligible; assented; dropped out and lost to follow-up will be calculated. To assess the feasibility of the media literacy intervention we will calculate intervention metrics (i.e., time spent on each piece of intervention content, percentage who complete all intervention content).

Acceptability measures. To assess acceptability, media literacy intervention participants will be asked to complete content ratings on each piece of intervention content using a 5-star rating system and an open text field. Participants will also be given the option of providing written feedback on each piece of content as well. All participants will also be asked to complete a satisfaction survey at the post-intervention follow-up.⁴⁸ Participants will be asked to report on study procedure acceptability (e.g., acceptability of recruitment, consent, assessment procedures). Intervention participants will be asked to report how informative, interesting, and helpful the intervention was; how likely they would be to recommend it to friends; and if they have suggestions for how it could be improved. Participants in the control group will be asked which website they went to, if any, and to report how informative, interesting, and helpful the website was; as well as how likely they would be to recommend it to friends. The satisfaction survey will include a combination of Likert scale and open-ended responses.

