**D. Website Design:**

[figure not shown]
- a. Description: The website is designed to mimic the flow and formatting of Netflix. It is adaptive so that it can be used on a mobile phone or a computer. There are tiles to represent the various parts of the intervention. There are three rows of tiles: recommended, completed, and locked. Once a participant has completed

recommended content, the tile for that content will move to the completed row and locked content will be unlocked and moved to recommended. Participants can complete pieces of content more than once and will be asked to rate each piece of content on a 5-star scale and provide additional comments about content (that can only be seen by them and our staff) upon their completion.

b. Screenshot of Site:

c. Screenshot of Example Feedback Panel:

[figure not shown]

d. Intervention Content

Topics	Intervention Content (Detailed Descriptions Below)
Male-Male Sex Ed 101	

Anatomy
 
 Penis Anus/Prostate 
HIV/AIDS and STIs Prevention
 
 HIV transmission 101 STI transmission 101 How to use a condom How to talk with sexual partners about STIs/HIV How to access services (e.g., testing, doctors) 
General Sexual Health
 
 The types of sex you can have with a male partner How to pick partners Anal health 
 Fiber/Anal douching How to safely and comfortably have anal sex How to use lubrication or lube (e.g., K-Y, bodyglide) Communication with partners Consent How to talk with sexual partners about what you would/would NOT like to do sexually Sex-seeking website/app etiquette/protection 	
 Sexual Health/Anatomy Animation by Blue Seat Studios Sexual Health/Anatomy Animation by Blue Seat Studios HIV/STI Jeopardy HIV/STI Jeopardy Sexual Health/Anatomy Animation by Blue Seat Studios Choose Your Own Dating Adventure Game HIV/STI Jeopardy Sex Menu Choose your own adventure communication overview Interview with [name] Interview with [name] Interview with [name] Interview with [name] Choose Your Own Dating Adventure Game Tea Consent Animation by Blue Seat Studios Choose Your Own Dating Adventure Game Choose Your Own Dating Adventure Game
Porn Literacy	

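### The daily, initialled PI check for reportable disclosures (6.1) covers satisfaction-survey free text but leaves out the comment field on each piece of website content

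*Combined protocol and SAP*

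**What the plan says.** In section 6.1 (Other considerations: Mental health and substance use), the protocol notes that none of its measures asks directly about reportable matters, but that "the satisfaction survey for the intervention will include open-ended responses". It continues: "The PI will check these open-ended responses daily in the unlikely event that a participant reports any indication of current, ongoing abuse". Neglect and imminent danger are covered in the same sentence, and the reason given is "as these indications will have to be considered for clinical intervention and mandated reporting to the appropriate authorities". The record of the review is also specified: "Daily checks will be documented via PI initials on a study calendar".

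Free text is collected in a second place. Section 4.2.1, after describing the star ratings of intervention content, adds: "Participants will also be given the option of providing written feedback on each piece of content as well". Section 11.2 describes the same ratings as "using a 5-star rating system and an open text field". Appendix 3, part D, says participants will be asked to "provide additional comments about content (that can only be seen by them and our staff) upon their completion". Section 11.2 places these ratings on the intervention website, whereas the assessments, including the satisfaction survey, are held in REDCap.

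**The concern.** The reason given for the daily check is that open text might reveal ongoing abuse, neglect or danger. That reason holds for any open text the study collects, and the check names only one of the two sources. A PI who followed 6.1 to the letter and initialled every day would never need to open the website comments.

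The participants are minors, and section 9 requests a waiver of parental consent, so the study's own safeguards carry more of the load. The comments are visible to staff, so the study would hold a disclosure whether or not anyone had been assigned to look for it. What is at stake is participant safety and the study's ability to show that it looked. Effect estimates, error rates and power are not involved.

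**Working it through.** The plan states no figure to reproduce. The check sets the free-text sources against the reviews that might cover them, then sizes the omitted source.

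**1. Are the two sources really separate?** Yes. Tables 1 and 3 list webpage ratings (during the intervention) and the satisfaction survey (post-intervention) as separate rows at different times. Section 11.2 puts them in different systems. The 6.1 wording points back to the survey mentioned just before it and cannot be stretched to the website field.

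**2. Which reviews reach the comment field?**

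| Review | Reaches website comments? | Frequency | Abuse/neglect purpose | Link to mandated reporting |
|---|---|---|---|---|
| 6.1, daily check | Not named | Daily, initialled | Yes | Yes |
| 6.1, PI monitoring of website data | Yes, through content ratings | Not stated | No | No |
| Table 2 and 10.2, adverse events | Website is a listed source; comments not named | Daily | Not named | No |
| 12.3, acceptability analysis | Open-ended responses inspected | Not stated | No | No |

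The real-time portal view in 6.1 is described only for aggregate page time and log-in counts. The adverse-event definition in 10.1 names suicidal behaviors, so danger to self is partly covered. It does not name a disclosure of abuse or neglect by someone else.

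**3. How many comment boxes?** Inputs: 75 intervention participants (section 9); 9 pieces described in Appendix 3 (items e to m); 10 distinct titles in the Appendix 3 topic table.

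- 75 × 9 = 675
- 75 × 10 = 750

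These are boxes offered if everyone completes each visible piece once. They are not an upper bound, because "Participants can complete pieces of content more than once" and the Appendix 3 text available for review may not show every piece. They are not an estimate of comments or disclosures either.

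**4. How much earlier can a comment be written?** Website access is emailed after baseline, and the survey email goes out three weeks after baseline (section 9).

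- Comment at first log-in (about day 0) to survey email: 3 × 7 = 21 days.
- To a reply at the end of the reminder period: 21 + 10 = day 31 if the 10 days include the first 3, or 21 + 3 + 10 = day 34 if they follow them.

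A participant who comments and never returns the survey gives the named check nothing to read.

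**5. Reading load of the fix.** Assume every box is used once and website activity lasts 10 to 52 weeks (70 to 364 days). The documents give only a 24-month total duration.

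- Lowest: 675 / 364 = 1.9 per day
- Highest: 750 / 70 = 10.7 per day

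That is about 2 to 11 short comments a day; fewer if boxes are left blank, more if content is repeated and commented on again.

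**The case against.** The strongest reply is that the field is already watched. Section 6.1 says the PI monitors and downloads website data and lists content ratings among them; 11.2 treats the text field as part of those ratings. Table 2 has the PI review adverse events daily with the website as a source. The adverse-event definition is open-ended and includes harmful behaviors, which could be read to include abuse. Section 10.2 adds day-to-day PI supervision, participants are told to contact the PI about symptoms or discomfort, and everyone receives crisis and support contacts. The duty to respond attaches to the indication itself, so a PI who happened on such a comment would still act.

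Much of this stands. The comments are not unmonitored, and the duty to respond is not limited to the survey. What remains is that no section gives a frequency for reading the comments, names abuse or neglect as something to look for there, or requires a record that anyone looked. Support contacts help the participant but do not alert the study.

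It is also fair to say that a field meant for reactions to a game or video may draw fewer disclosures than a general survey question. The documents give no rate for either, and the protocol itself regards such reports as unlikely. The 21- to 34-day intervals show how much earlier the omitted source is, not a measured delay in detection: the survey answer need not repeat the disclosure, and no survey closing date is stated.

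**Conclusion.** The concern holds as a narrow gap in participant-safety procedure. The intervention arm has two free-text sources, and the one documented check tied to mandated reporting names one of them. The omitted source is confined to the intervention arm, is open earlier than the survey, and offers 675 to 750 boxes on first completion of the visible content. The probability of a reportable comment is unknown and probably low; the consequence of missing one from a minor could be serious; the remedy is trivial. It should be fixed.

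The textual omission does not depend on any assumption. The box count assumes full completion of the 9 or 10 visible pieces by all 75 participants, and the reading load also assumes 10 to 52 weeks of website activity. Nothing here bears on outcomes or power.

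**What to change.** Amend section 6.1 so that the initialled daily PI check covers the website comment field as well as the satisfaction-survey free text. What is done when a disclosure is found can stay with the investigator and the IRB.

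The cost is one sentence of amendment, a daily export of the comment field, and PI time for roughly 2 to 11 comments a day under the assumptions above. No extra staff are needed.

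Two points are worth confirming at the same time, as queries only: that control-arm survey free text falls within the check, and whether the sexual abuse history subscale in 11.2 could pick up current abuse.

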6.2 Potential Benefits

The largest anticipated benefit is from participating in the YM&M intervention. We expect that individuals who complete the YM&M intervention will gain insight into their sexual health and SEOM consumption that could lead to sustained sexual behavior and attitude change.

By participating in the research, participants will also benefit from knowing they may ultimately be helping others to reduce their risk behaviors. Possible risks are likely to be outweighed by the new knowledge gained regarding the potential of this approach to reduce HIV risk and increase the sexual well-being of ASMM. The risks of participating in the research will be minimized through our extensive efforts to maintain confidentiality and to reduce discomfort or distress.

6.3 Analysis of Risks in Relation to Benefits

We expect the benefits will outweigh the risks of participating in this research. In previous research conducted by the PI many participants have reported that they enjoyed participating. In addition, some participants noted that completing self-report assessments, which ask them to reflect on their health behaviors, was a helpful experience; based on previous research, it is likely that the act of filling out detailed health behavior assessments can result in positive health behavior changes.

7 Study Subject Selection

A convenience sample of ASMM ($N = 150$) from across the US will be recruited online through social media.

7.1 Subject Inclusion Criteria

In order to be eligible to participate in this study, an individual must meet all of the following criteria:

- Be age 14 to 17.
- Report having been assigned male sex at birth and self-identify as male (i.e., be cisgender male).
- Self-identify as gay/bisexual, report being sexually attracted to males, or report having voluntary sexual contact with a male partner in the past year.
- Have intentionally accessed SEOM in their lifetime.
- Have a valid personal email address.
- Be a US resident.
- Be new to the study.

All inclusion criteria will be determined via self-report except for having a valid email address. Having a valid email address will be determined by requiring participants to use a unique link sent to their personal email address to access the assessments.

7.2 Subject Exclusion Criteria

An individual who meets any of the following criteria will be excluded from participation in this study:

- Are unwilling or unable to provide informed assent, which would preclude meaningful participation in the research.
- Are unable to understand and read English. Participants who are unable to understand and read English will not be included because they would not be able to complete the assessments nor would they benefit from the intervention.
- Do not have the appropriate device and necessary software to allow them to experience all the intervention content. Because (a) 94% of sexual minority adolescents reporting at least daily Internet use⁶¹ and (b) participants will be recruited from websites that are likely to have similar device and software requirements, this

criterion should not limit our sample. A recent online sexual health education pilot intervention targeting LGBT adolescents (ages 16-20) had a similar requirement and found that only 4% of the 1,734 potential participants who completed their eligibility screener were ineligible due to the technology requirements.⁵³

8 Study Intervention

Four main topics areas were identified by youth in our previous survey^{24,26,45,45-47} and the youth advisory board as important foci for the intervention: (1) male anatomy, including information about how anal sex can be pleasurable and about anal health; (2) HIV/STI prevention information (e.g., transmission risks, accessing testing, condom use); (3) general sexual health information (e.g., types of male-male sex, consent, dating safety, partner communication); and (4) SEOM literacy (e.g., differences between porn and reality, what's behind the scenes on a pornography set, normalization of porn use among male youth). Youth felt that intervention content should be interactive (e.g., games, videos, animations) and the website should have an interface that would be familiar to ASMM (e.g., similar to Netflix). Youth preferred a website with a responsive design (i.e., will work on a mobile device, tablet, or computer) as opposed to a downloadable phone application. Please see Appendix 3 for screen shots from the intervention website and a more detailed description of the content.

9 Study Procedures

Overview

- **Recruitment, screening, and assent (described in more detail below):** Participants will be recruited via online advertisements. Once they click on an advertisement they will be presented with information about the study and a brief online screener to establish eligibility. If they are eligible they will be presented with assent materials and complete capacity to assent questions. If they agree to participate they will then be emailed a unique link to the baseline assessment.
- **Baseline assessment:** Participants will be sent an email with a link to a self-report online survey ($N = 150$; Approx. 25-35 minutes); compensation for time (\$15 electronic gift card via email). If participants do not complete the baseline assessment within three days of assenting, we will send them up to 3 reminder emails in a 10-day period.
- **Randomization:** immediately following the final question in the baseline assessment, REDCap⁶⁰ will be programmed to randomly assign participants (1:1 randomization) to the YM&M intervention or to a control group. The randomization schedule will be generated using a permuted block randomization procedure with small, randomized blocks.
 - Participants randomized to the YM&M ($n = 75$) intervention will be sent an email with username (their email) and a temporary password and asked to complete all of the website content within three weeks of receiving the email. Participants will be asked at first log-in to set up their own password. If a participant has not logged into the website within one week of receiving the original email, they will be sent up to 3 reminder emails in a 10-day period.
 - Participants in the control condition ($n = 75$) will be sent an email with links to various HIV prevention websites (e.g., the CDC HIV Prevention site, the National HIV and STD Testing Resource site) and encouraged to visit at least one site in the next three weeks.
- **YM&M intervention exposure:** Intervention content, language, and length was informed by a youth advisory board and a previously completed online survey.^{24,26,45,45-47} Although the intervention is designed to be completed in one sitting (i.e., < 90 minutes in length), participants will be given the option of logging out and logging in again to continue where they left off, should they need to. Intervention content is described in more detail above and in Appendix 3.
- **Post-intervention assessment:** Three weeks after the baseline survey participants will be sent an email to complete a second online survey ($N = 150$; Approx. 15-25 minutes); compensation for time (\$25 electronic gift card via email). If participants do not complete the post-intervention assessment within three days of receiving the email, we will send them up to 3 reminder emails in a 10-day period.
- **Follow-up assessment:** Fifteen weeks after the baseline survey participants will be sent an email to complete a final online survey ($N = 150$; Approx. 20-30 minutes); compensation for time (\$35 electronic gift card via email). If

participants do not complete the follow-up assessment within three days of receiving the email, we will send them up to 3 reminder emails in a 10-day period.

- **All participants:** Participants will be offered a bonus if they complete all assessments (\$20 electronic gift card via email). All participants will receive a list of youth-oriented resources at the end of the survey or if they are ineligible (Appendix 4).

Detailed description of recruitment, screening, assent, and retention procedures.

Recruitment Processes. Participants will be recruited using advertisements and posts on social networking websites (e.g., Facebook, Instagram, Snapchat). Potential participants recruited via advertisements will be directed to the screening website which will assent them for screening and then ask potential participants to continue on for eligibility questions.

Screening Procedures. Study eligibility will be determined via inclusion criteria questions (nested among foil questions so that these criteria are not obvious) and cross verified using additional questions throughout the survey. Eligibility screening will occur on the screening website, which will be hosted and created using REDCap,⁶⁰ a highly secure online survey program. To protect against the possibility of multiple enrollment of the same participant, eligibility screening information will be cross-referenced against: date of birth, age, race/ethnicity, and geographic location.^{62,63} Online advertisements and the eligibility screener will not indicate the necessary requirements for eligibility in order to minimize the potential for faking eligibility.⁶⁴ To ensure ethnic and racial diversity, eligibility criteria and advertisements will be adjusted to oversample racial/ethnic minority participants, as needed.⁶⁵ Screening data will be retained for eligible and ineligible individuals as described in the assent for screening.

Assent Procedures. In line with ethical recommendations^{66–70} and standard practice^{5,6,15,24,26,45,53,59,71–75} for sexual health research with LGBT adolescents, a waiver of parental consent is being requested to decrease risk to participants and ensure validity of the results. Parental consent would decrease participation rates because some youth will fear that they may be “outed” (i.e., involuntary disclosure of their sexual minority status) as a result of participation. Specifically, disclosure of sexual preferences may place some participating youth at risk for parental disapproval leading, in some instances, to harassment, abuse, or even expulsion from the home.^{45,58,76–79} Recent research by the CDC reports that ASMM commonly experience homonegativity which leads to internalized homonegativity, HIV stigma, silence about homosexuality, and forced housing displacement due to their sexual orientation, which, in turn, leads to increased risk for HIV seroconversion. This is especially true for racial/ethnic minority ASMM.⁸⁰ It is crucial that the proposed research reach these high-risk ASMM.

The nature and scope of the proposed research does not pose more than “minimal risk” to participants (45 CFR Part 46.102) (i.e., “that the probability and magnitude of harm or discomfort anticipated in the research are not greater in and of themselves than those ordinarily encountered in daily life or during the performance of routine physical or psychological examinations or tests”). Study measures and exposure to sexual health topics are standard in this population, as are waivers of parental permission.^{5,6,15,24,26,45,53,59,71–75} The majority of adolescents will have received some form of formal sexual education by the time they are 14 years old.⁸¹ Thus, the proposed intervention will most likely not be a participant’s first exposure to formal sexual health education and instead will be an ASMM-specific supplement to the sexual health education they have already received. Additionally, only participants who self-report have voluntarily been exposed to SEOM will be included. Participants will not be exposed to SEOM as a part of this study. Further, all 50 states plus the District of Columbia allow most minors 14 years old or older to consent to STI services without parental permission.⁸² Similarly, youths of any age can buy condoms without parental consent.

To compensate for waiver of parental consent, participants will receive a formal assessment of capacity to assent (described below) to ensure their understanding of study goals, procedures, and risks from disclosure of sensitive information. Further assent material will include a table clearly outlining the pros and cons of participation. Consistent with national policy recommendations from the Society for Adolescent Medicine and the American Psychological Association,^{83,84} requiring parental permission for the proposed study would have a number of possible negative effects, including: (1) reducing the validity of the findings by effectively eliminating potential participants unwilling to share permission forms with their parents/guardians; (2) increasing risk to youth whose parents would have a negative

response to the material in the permission forms that would correctly suggest their child has a minority sexual preference; and (3) adding little in the way of actual subject protection, given the minimal risk of study participation.^{45,58,76–79} The procedures for the waiver of parental consent are consistent with the guidelines provided by the Department of Health and Human Services (45 CFR Part 46, Subpart D).

There will be two assent procedures as a part of the study: (1) assent for screening and (2) assent for the full study. Both of those assent procedures will occur online and affirmation of desire to take part in either the screening or full study will be shown by potential participants clicking acknowledgment that they would like to proceed.

When a potential participant clicks on a study advertisement they will be portalled to the assent for screening materials. Those materials will describe screening procedures, confidentiality, and subject rights. At the end, potential participants will be asked to indicate whether they would like to move on to eligibility questions or not, which is the documentation of their decision to proceed with the screening.

Assent procedures for the full study will describe the study, its risk and benefits, confidentiality, no deception, and how to contact the investigators. The assent process will highlight that potential participants have the option of refusing to participate in the study, withdrawing their participation at any time, and/or refusing to answer any questions that they feel uncomfortable responding to. Further, potential participants will be informed that their decision to participate or not participate in the study will not affect their relationship with any websites, LGBT youth-oriented CBOs, clinics, or Boston University. Capacity to assent will be further confirmed by administering multiple choice questions that will evaluate participants' ability to: (1) name things they will be expected to do during the study, (2) explain how they will be assigned to their group, (3) explain what they would do if they experienced distress during the study, and (4) identify potential risks for participating in the study.^{85,86} Participants who are unable to accurately answer the multiple choice questions will be redirected to the relevant portions of the assent materials and asked the questions again. Capacity to assent questions and answers will be automatically re-ordered each time they are presented to reduce the chance of participants blindly choosing answers until they get the right ones. Participants will be given three chances to correctly answer capacity to assent materials. If after three chances they continue to answer questions incorrectly they will be considered ineligible. Potential participants will be given the option of contacting study staff (via e-mail, telephone number, and mailing address) to ask questions before enrolling. After potential participants have been determine to have capacity to assent they will be asked whether they would like to participate in the study or not, which is the documentation of their decision to enroll in the study. Once eligible participants have assented they will be sent an email containing a unique link to the baseline survey. To proceed to the main body of the survey, eligible participants will be required to click on that link. Participants will be reminded about assent parameters at the start of each follow-up assessment.

Retention Plan. Retention strategies include participant reminders, repeated contact, and compensation. Eligible participants who provide assent will be asked to provide an email address and phone number(s) for recontacting/tracking. REDCap will maintain an electronic system that will notify participants via email when they are due for an assessment and remind them up to 3 times within a 10-day period if they have missed an assessment. Participants will have the option to discontinue the study at any point by contacting study staff. Participants who wish to drop out of the study will be queried as to their reasons and attempts will be made to address their concerns. Participants will be compensated at the completion of the baseline survey (\$15) and after each of the follow-up surveys (\$25 for post-intervention, \$35 for follow-up). Participants will be offered a bonus for the completion of all surveys (\$20). Participants will be compensated via electronic gift cards.

See the Appendix 2 for the schedule of events.

10 Assessment of Safety and Data Safety Monitoring Plan (DSMP)

